Safety Variables	The frequency of TEAEs, TEAEs leading to withdrawal from study, treatment-emergent SAEs, AEs of special interest, clinically significant abnormal laboratory test results, audiology test results, and vital signs measurements
Statistical Methods	Sample Size Determination

Protocol Amendment 3.1: 25 May 2017

*This protocol is solely for communicating information about the investigational drug between Insmmed Incorporated and study personnel. Information is not to be reproduced, abstracted or used for sharing of information for any other purpose, whatsoever, except with the written permission of Insmmed Incorporated.*

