All subjects will have routine visits at Day 1, Months 1, 2, 3, 4, 5, 6, 7, 8, 9, 10, 11, and 12/EOT. At these visits, vital signs, pulse oximetry, and urine pregnancy test (if woman of child bearing potential) will be performed. Safety laboratory assessments (chemistry, hematology, and urinalysis) and a healthcare resource utilization questionnaire will be conducted at Day 1, Months 1, 3, 6, 9, and 12/EOT. Physical examination and body weight measurements will be conducted at Day 1, Months 1, 3, 6, 9, and 12/EOT. The 6MWT, audiology test, SGRQ, and EQ-5D-3L will be assessed at Day 1 and Months 6 and 12/EOT.

**Any procedure performed at EOT in the INS-212 study will be used as the Baseline (Day 1) measurement for this study and will not need to be performed a second time.** It is possible and acceptable that procedures in INS-212 will be performed prior to the INS-312 informed consent being signed.

Home Healthcare visits may be available at Months 2, 4, 5, 7, 8, 10, and 11 for sites with IRB/EC approval to conduct Home Healthcare visits, and for qualifying subjects who may have difficulty attending clinic visits.

[figure not shown]
All subjects will return 1 month after their EOT to have an off-LAI treatment follow-up visit (EOS: End of Study) performed; this includes subjects who early terminate the study as both the EOT and EOS visits will need to occur. At this visit, a physical examination (including vital signs, pulse oximetry and weight), SGRQ, and EQ-5D-3L will be performed.

Unscheduled visits will occur as needed should subjects' symptoms worsen between visits.

Protocol Amendment 3.1: 25 May 2017

*This protocol is solely for communicating information about the investigational drug between Insmad Incorporated and study personnel. Information is not to be reproduced, abstracted or used for sharing of information for any other purpose, whatsoever, except with the written permission of Insmad Incorporated.*

Figure 3-1 Study Design

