## 9.6 SAFETY ANALYSIS

The safety endpoints are the frequency of TEAEs, TEAEs leading to withdrawal from study, treatment-emergent SAEs, AEs of special interest, clinically significant abnormal laboratory test results, and vital signs measurements. The safety analysis will be performed for the safety population.

All AEs will be coded using the Medical Dictionary of Regulatory Activities (MedDRA). AEs starting between first study drug administration and 1 month after last study drug administration will be regarded as treatment emergent (TEAE).

The number and percentage of subjects with TEAEs, TEAEs leading to withdrawal from study, and treatment-emergent SAEs will be tabulated by System Organ Class and Preferred Term overall and by the assigned treatment arm in INS-212. Furthermore, the incidence of TEAEs by worst grade of severity will also be tabulated by System Organ Class and Preferred Term overall and by assigned the treatment arm in INS-212.

AEs that are not treatment-emergent will be listed.

For all other safety data (vital sign measurements, clinical laboratory values, and physical examination findings) observed values and changes from Baseline for continuous variables, absolute and relative frequencies for categorical observations, and shift tables from Baseline to last observation will be summarized overall and by the assigned treatment arm in INS-212 using descriptive statistics.

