3.2. Study Endpoints

3.2.1. Primary Endpoints

The primary endpoint is the frequency of treatment-emergent adverse events (TEAEs), TEAEs leading to withdrawal from study, treatment-emergent serious adverse events (SAEs), AEs of special interest, clinically significant abnormal laboratory test results, and vital signs measurements. The primary endpoint will evaluate the overall population and describe the subjects by treatment arm assigned in the INS-212 study (ALIS added to a multi-drug regimen arm and a MDR alone).

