6. GENERAL CONSIDERATIONS FOR DATA ANALYSES AND HANDLING

6.1. Data Presentation Conventions

Continuous variables will be summarized with means, standard deviations, medians, minimums, and maximums, and, if appropriate, by clinically relevant discretization's. Categorical variables will be summarized by counts and by percentage of subjects in corresponding categories. All data that meaningfully contribute to the objectives of the study will be included. Footnotes will specify the basis for the percentages. For counts of subjects, however, the denominator will generally be the number of subjects in the Safety population and treatment arm (based on treatment assignment in INS-212). All summary tables will be presented by treatment arm. A total summary column may be included in some summary tables wherever relevant.

Summaries of continuous variables that have some values recorded using approximate values (e.g., < or >) will use the numeric part of the value in calculations. Listings will present the data in its original format.

For summaries where rounding is required, rounding will be done to the nearest roundoff unit. For example, if the round-off unit is the ones place (i.e., integers), values $\geq XX.5$ will be rounded up to $XX+1$ while values $< XX.5$ will be rounded down to XX .

Individual subject data obtained from the electronic case report forms (eCRFs), and any derived data will be presented by treatment, site, and subject in data listings.

An unscheduled visit can be used in the determination of baseline values, if it provides the last non-missing value prior to the first dose of the study drug. Post-baseline unscheduled visit data will be presented in the listings only (i.e., unscheduled visit data will not be summarized in tables). If subject has more than one data at a specific visit for any reason, average of the data at that visit will be considered in summary tables.

The analyses described in this plan are considered a priori, in that they have been defined prior to database lock. Any other analyses performed will be considered post-hoc. Posthoc analyses will be labeled as such on the output and identified in the CSR.

All analyses and tabulations will be performed using SAS[®] version 9.4 or higher. Tables, listings, and figures will be created in rich text format.

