9.5. Routine Laboratory Data

All clinical laboratory data summaries and tabulations will be based on the safety population.

At each visit, only those subjects providing data at the visit will appear on the tables.

The actual, baseline and change-from-baseline of the clinical laboratory results (blood chemistry and hematology) will be summarized (n, mean, standard deviation, median, minimum, and maximum) by visit for each prior treatment and total groups. At each visit the baseline summary will reflect those subjects who provided data at that visit.

Shifts-from-baseline-to-visit in categorization of result by normal ranges (low, normal, high, total) will be tabulated clinical laboratory results (blood chemistry and hematology) presenting the number and percentage of subjects in each cell. These shift tables will also be presented for clinically significant labs.

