7. GENERAL ANALYSIS CONSIDERATIONS

The statistical analyses will be reported using summary tables, listings, and figures, with subjects classified per their assigned INS-212 treatment. The ICH numbering convention will be used for all outputs. Unless otherwise noted, all statistical testing (if any) will be two-sided and will be performed at the 0.05 significance level. Tests will be declared statistically significant if the calculated p-value is < 0.05 .

Continuous variables will be summarized with means, standard deviations, medians, minimums, and maximums. Categorical variables will be summarized by counts and by percentage of subjects in corresponding categories. All data that meaningfully contribute to the objectives of the study will be included. Footnotes will specify the basis for the percentages. For percentages of subjects, the denominator will generally be the number of subjects in the analysis set and INS-212 treatment arm. All summary tables will be presented by INS-212 treatment arm. A total summary column may be included in some summary tables where relevant.

Summaries of continuous variables that have some values recorded using approximate values (eg, $<$ or $>$) will use the numeric part of the value in calculations. Listings will present the data in its original format.

For summaries where rounding is required, rounding will be done to the nearest round-off unit. For example, if the round-off unit is the ones place (ie, integers), values $\geq XX.5$ will be rounded up to $XX+1$ while values $< XX.5$ will be rounded down to XX .

Individual subject data obtained from the electronic case report forms (eCRFs), and any derived data will be presented by site, INS-212 treatment arm and subject in data listings.

Post-baseline unscheduled visit data will be presented in the listings only (ie, unscheduled visit data will not be summarized in tables). If a subject has more than one observation at a visit for any reason, the average of the observations will be used in summary tables.

The analyses described in this plan are considered a priori, in that they have been defined prior to database lock. Any other analyses performed will be considered post-hoc. Post-hoc analyses will be labeled as such on the output and identified in the CSR.

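### Laboratory, vital-sign and audiology tables leave out unscheduled post-baseline values and average repeats, and no planned table shows a subject's worst value

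*SAP*

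**What the plan says.** Two general rules in final SAP 6.1 govern the tables. On unscheduled data: "Post-baseline unscheduled visit data will be presented in the listings only (i.e., unscheduled visit data will not be summarized in tables". On more than one value at a visit: "average of the data at that visit will be considered in summary tables". Section 7 of the SAP for the initial analyses has the same rule on unscheduled data ("Post-baseline unscheduled visit data will be presented in the listings only (ie, unscheduled visit data will not be summarized in tables") and also averages repeats.

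The safety sections of the final SAP add no exception:

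- **Laboratory (9.5):** by-visit summaries and "Shifts-from-baseline-to-visit" tables in low, normal and high categories. The same shift format is used for clinically significant results.
- **Vital signs (9.6):** by-visit summaries, with pre-dose and post-dose as separate timepoints. There is no shift table.
- **Audiology (9.7 and the table list in 11.1):** decibel summaries, CTC grade counts and a grade shift table, the last two by visit.

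The primary endpoint in final SAP 3.2.1 names "clinically significant abnormal laboratory test results, and vital signs measurements" next to the adverse event components. Audiology is not on that list. The protocol synopsis gives it as a safety variable: "clinically significant abnormal laboratory test results, audiology test results, and vital signs measurements". Protocol 9.6 plans "shift tables from Baseline to last observation will be summarized overall" for laboratory values and vital signs.

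**The concern.** Protocol 3.1 says "Unscheduled visits will occur as needed", and the trigger it gives is worsening symptoms between visits. Any measurements taken at such visits are more likely than routine ones to be abnormal, yet they appear only in listings. Averaging has a similar effect: an abnormal result followed by a normal repeat is pulled towards normal before it is categorised.

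By-visit tables also do not answer the question the endpoint asks. A frequency of clinically significant laboratory abnormality is naturally the number of subjects with at least one such result after baseline. The plan provides no such count, even from scheduled data.

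The SAP does make exceptions elsewhere. An unscheduled value may set the baseline (6.1), and an unscheduled positive culture defeats culture conversion (6.4.10). Post-baseline safety values get no matching treatment. At stake is whether the numeric safety tables of a long-term safety study show how far subjects' values actually moved.

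**Working it through.** The plan states no figure on this point, so there is none to reproduce. The check sets the rules against the schedule and then illustrates their effect.

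**1. Scheduled coverage.** Assessment visits come from the schedule of events and target days from Table 4 of the final SAP.

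| Data | Target days | Gaps (days) |
|---|---|---|
| Chemistry, hematology | 1, 30, 90, 180, 270, 365 | 29, 60, 90, 90, 95 |
| Audiology | 1, 180, 365 | 179, 185 |
| Vital signs to Month 12 | 1, 30, then monthly to 330, 365 | 29 to 35 |

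A value measured at an unscheduled visit inside one of these gaps enters no laboratory, vital-sign or audiology table.

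**2. Averaging in the laboratory shift tables.** Assume that 'high' means above 1 x ULN. The pairs are hypothetical.

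- 1.3 and 0.7: (1.3 + 0.7)/2 = 1.0. The worst value is high and the tabulated value is not.
- 1.2 and 0.9: (1.2 + 0.9)/2 = 1.05. Still high.
- 2.2 and 1.0: (2.2 + 1.0)/2 = 1.6. Still high.

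Averaging can remove a category but does not always do so.

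**3. Averaging in hearing grades.** In Table 3 of the final SAP, Grade 1 is a shift of 15 to 25 dB and Grade 2 is above 25 dB. Two readings of 30 and 20 dB would average (30 + 20)/2 = 25.0 dB, which is Grade 1 instead of Grade 2. Readings of 35 and 20 dB would average 27.5 dB and stay Grade 2. No stated procedure produces two audiograms at one visit, so this shows only what the rule would do.

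**4. Leaving out unscheduled values.** Let N be the number of subjects, p the share with any abnormal value, and s the share of those whose only abnormal value is unscheduled. Then tabulated count = N x p x (1 - s). N = 200 is the expected enrolment in Protocol 3.6.1; p and s are assumptions. For example, 200 x 0.10 x (1 - 0.30) = 14.

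| p | Any-time count | s = 10% | s = 30% | s = 50% |
|---|---|---|---|---|
| 5% | 10 | 9 | 7 | 5 |
| 10% | 20 | 18 | 14 | 10 |
| 20% | 40 | 36 | 28 | 20 |

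The proportional loss equals s by construction, and the documents give no value for s.

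**5. Protocol 9.6 against the final SAP.** The protocol's shift runs from baseline to last observation and covers vital signs. The final SAP has by-visit laboratory shifts and no vital-sign shift, and sections 9.5 and 9.6 give no reason for the difference.

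**The case against.** The strongest reply is that adverse event reporting already covers what matters, and much of it stands. Protocol 7.1.1 collects events at every contact. Final SAP 9.2.1 counts a subject who reports an event at least once, with highest-grade tabulations. Laboratory abnormalities that the investigator finds clinically relevant are AEs (Protocol 8.1). Significant vital-sign findings after the first dose that meet the AE definition must be recorded as AEs (7.1.3), and so must hearing loss of Grade 2 or higher (7.1.6). The AESI list includes raised creatinine, reduced glomerular filtration rate and hypoacusis.

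A reader might therefore infer too much in four ways:

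- **That unscheduled findings vanish from every table.** They do not: the AE, SAE and AESI tables are event-based.
- **That the primary endpoint as a whole misses the worst values.** Its AE components do not depend on visits. Only its laboratory and vital-sign tables are affected, and hearing enters only through adverse events.
- **That averaging ALT of 4 and 1 x ULN to 2.5 changes a table.** It does not: 4 and 2.5 are both high, and the protocol's 3 x ULN figure belongs to eligibility and withdrawal criteria.
- **That repeat audiometry after Grade 2 is discarded or averaged.** Protocol 7.1.6 places it at the next scheduled visit, so neither rule applies.

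Three further limits stand. Pre-dose and post-dose vital signs are not averaged together. The final SAP does not say that a clinical-significance flag is rederived from averaged values. The schedule prescribes no procedures for unscheduled visits, so the volume of excluded data is unknown.

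AE reporting still does not replace the numeric tables. It depends on investigator judgement for laboratory values and becomes mandatory for hearing loss only at Grade 2. The laboratory and vital-sign components are listed separately from the adverse events. A shift to last observation would not capture the worst value either. Its replacement is a separate departure from the protocol, and a small one for laboratory data when an EOT sample exists.

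**Conclusion.** The point holds for the laboratory, vital-sign and audiology summaries. Read as written, the rules keep unscheduled post-baseline values out of these tables and average repeats, and nothing planned restores the extreme. The clinically significant laboratory results, a primary-endpoint component, can be undercounted. What is lost is the objective worst value and any abnormality that was not reported as an AE.

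The loss is possible, not demonstrated. It depends on how many abnormal values are unscheduled only and how often values are repeated within a visit, and the documents give neither. The counts above illustrate a range of assumptions and do not estimate this study's loss. The data remain in listings, so nothing is irrecoverable. The documents do not support a claim that the primary safety endpoint fails. They support a change to the tabulation rules that should be made.

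**What to change.** Before database lock, amend final SAP 6.1 and 9.5 to 9.7:

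1. Add baseline-to-worst-post-baseline shift tables for chemistry, hematology and vital signs, and a table of worst CTC hearing grade. Use all scheduled and unscheduled on-treatment values, with the on-treatment window stated.
2. Count a subject as having a clinically significant laboratory result if any post-baseline result qualifies.
3. Exempt safety categories from averaging: for repeats at a visit, use the worst value in shift and grade tables. The by-visit means can stay as planned.
4. Provide the baseline-to-last-observation shift tables of Protocol 9.6, including vital signs, or state the deviation and the reason.

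The cost is a few extra tables from data already collected and listed. Abnormality counts may rise slightly, and the table notes should say that worst-value tables include unscheduled results. If the tables are added after lock, the SAP's own rule requires them to be labelled post-hoc.

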6.2. Analysis Populations

6.2.1. Safety Population

The safety population is the set of subjects who received at least 1 dose of ALIS.

6.3. Baseline Definition

Any non-missing value from any procedure at a subjects EOT visit in study INS-212 will be denoted as their baseline value. If that result from the aforementioned visit is missing, then the non-missing value at the subsequent visit in the INS-312 study.

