6.4.6. Change-from-baseline

Change-from-baseline is calculated as (post-baseline result – baseline result).

Percent change-from-baseline is calculated as (100 * change-from-baseline/baseline result).

If either the baseline or the post-baseline result is missing, the change-from-baseline and percentage change-from-baseline are also missing.

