6.4.9. Visit Windows

Nominal visit windows will be used for all visits, except for EOT and EOS visits. Because EOT and EOS visits are conducted in place of the planned visit for subjects who prematurely end treatment or study participation, these visits also need to be mapped to the coincident visit.

For example, a subject discontinues treatment at the Month 4 visit. The site will conduct the EOT visit at Month 4 rather than the Month 4 visit, but for analysis purposes this visit should be used for the Month 4 summary as well as the EOT summary. Similarly, for the EOS visit. Thus, should it be appropriate, the EOT and EOS visit need to be mapped to the corresponding visit. Should the EOT or EOS visit map to a time that doesn't coincide with a scheduled visit, it will not be mapped.

Subjects who prematurely discontinue from the study, may not have an EOT visit. In this case the EOS visit will also be the EOT visit and should be mapped accordingly.

Table 4: Visit Windows (Days)

Visit Name	Visit Number	Target Anchor	Relative Target Day	Visit Window
Baseline	1	Last visit from Study INS-212	1	-2 to 1
Month 1	2		30	23 to 37
Month 2	3		60	53 to 67
Month 3	4		90	83 to 97
Month 4	5		120	113 to 127
Month 5	6		150	143 to 157

Visit Name	Visit Number	Target Anchor	Relative Target Day	Visit Window
Month 6	7		180	173 to 187
Month 7	8		210	203 to 217
Month 8	9		240	233 to 247
Month 9	10		270	263 to 277
Month 10	11		300	293 to 307
Month 11	12		330	323 to 337
Month 12 (EOT)	13		365	353 to 367
Month 13 (EOS)	14		420	413 to 427

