9.6. Vital Signs

All vital signs data summaries and tabulations will be based on the safety population.

At each visit, only those subjects providing data at the visit will appear on the tables.

The actual, baseline and change-from-baseline of the vital signs will be summarized (n, mean, standard deviation, median, minimum, and maximum) by visit and timepoint (pre-dose and post-dose) for each prior treatment and overall. At each visit the baseline summary will reflect those subjects who provided data at that visit.

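### Final SAP 6.3 sets no pre-dose condition on the fallback Baseline: read literally it can use an on-treatment Month 1 value, and on Day 1 it leaves the vital-sign and oximetry Baseline open (minor)

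*SAP*

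**What the plan says.** The SAP file holds two plans: the final (confirmatory) SAP and the SAP for the first analysis. The point concerns the final one.

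- **Final SAP 6.3** takes any non-missing INS-212 EOT value as Baseline. The fallback is: "If that result from the aforementioned visit is missing, then the non-missing value at the subsequent visit in the INS-312 study".
- **Final SAP 6.1** lets an unscheduled visit supply Baseline only "if it provides the last non-missing value prior to the first dose of the study drug". This is the only pre-dose wording in the final SAP's derivation rules for Baseline. The same section says that where a subject has several values at a visit, the "average of the data at that visit will be considered in summary tables".
- **Final SAP 6.4.9, Table 4** anchors Baseline to "Last visit from Study INS-212", with a window of Day -2 to 1. The Month 1 window is Day 23 to 37.
- **Final SAP 6.4.6**: "If either the baseline or the post-baseline result is missing, the change-from-baseline and percentage change-from-baseline are also missing".
- **Final SAP 9.6** summarises vital signs "by visit and timepoint (pre-dose and post-dose) for each prior treatment and overall", without saying which timepoint is Baseline.
- **Protocol synopsis (design figure footnote)** and **first-analysis SAP section 3** make the INS-212 EOT visit and INS-312 Day 1 the same visit.
- **Protocol 6.1** has procedures not already done at INS-212 EOT carried out at Visit 1, where the first dose is also given.

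**The concern.** A Baseline for a safety summary should come before the exposure being assessed. Section 6.3 does not ensure this, and its wording can be programmed in two ways.

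If the next INS-312 visit means Visit 1, the problem is confined to vital signs and oximetry. These are measured before and after the Day 1 dose, so Baseline could be the pre-dose value, the post-dose value or their average.

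If INS-212 EOT already is INS-312 Day 1, the next visit is Month 1. Baseline is then an on-treatment value for chemistry, hematology, vital signs or weight. That subject's Month 1 change is 0 by construction, and later changes lose whatever happened between Day 1 and Month 1. The laboratory tables report "Shifts-from-baseline-to-visit in categorization of result by normal ranges". A result that rose above range before Month 1 would be shown as high at Baseline, and so would not appear in a normal-to-high cell while it stays high.

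The primary endpoint includes "clinically significant abnormal laboratory test results, and vital signs measurements", so these summaries support the main safety description.

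**Working it through.** The plan states no figure for this point, so there is none to reproduce. The check sets the passages side by side and then sizes the effect on stated assumptions.

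**1. Which Baseline each reading gives**

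| Measure | Visit 1 reading | Month 1 reading |
|---|---|---|
| 6MWT, SGRQ, EQ-5D-3L | Pre-dose (Protocol Table 3-1 note) | Not measured at Month 1; change missing under 6.4.6 |
| Audiology | Pre-dose (Table 3-1 footnote f) | Not measured at Month 1; change missing under 6.4.6 |
| Weight, with physical examination | Pre-dose (Protocol 7.1.4.1) | On-treatment value |
| Chemistry, hematology | Pre-dose (Protocol 7.1.2.1) | On-treatment value |
| Vital signs, oximetry | Pre-dose, post-dose or average: not settled | On-treatment value, same choice open |

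**2. Timing of a Month 1 Baseline.** Days since first dose = study day - 1, taking the first dose on study day 1. The window of Day 23 to 37 gives 22 to 36 days; the target day 30 gives 29. All lie outside the Table 4 Baseline window.

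**3. Size on the Month 1 reading.** Inputs: N is about 200 (Protocol 3.6.1). The share affected, m, is not in the documents; 1%, 2% and 5% are assumed. Missingness is taken as unrelated to the change. The true normal-to-high rate r at Month 1 is assumed to be 5% or 10%.

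- Subjects affected: 200 × m = 2, 4, 10.
- Overall mean Month 1 change, as a fraction of the true change: 1 - m = 0.99, 0.98, 0.95.
- Displayed normal-to-high rate: r × (1 - m). For r = 5%: 4.95%, 4.90%, 4.75%. For r = 10%: 9.9%, 9.8%, 9.5%.
- Expected subjects in the wrong shift row: 200 × m × r, from 200 × 0.01 × 0.05 = 0.1 to 200 × 0.05 × 0.10 = 1.0.

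**4. Size on the Visit 1 reading.** Let d be the change in oximetry after the Day 1 dose; it is not in the documents, and 1 to 3 points is assumed. Relative to the pre-dose value, Baseline differs by 0 (pre-dose), d/2 (average) or d (post-dose). For d = 2, an affected subject's later changes move by 0, 1 or 2 points. With a post-dose Baseline the overall mean change moves by m × d:

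| | m = 1% | m = 2% | m = 5% |
|---|---|---|---|
| d = 1 | 0.01 | 0.02 | 0.05 |
| d = 2 | 0.02 | 0.04 | 0.10 |
| d = 3 | 0.03 | 0.06 | 0.15 |

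Averaging halves these.

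**The case against.** The best defence is that Visit 1 is plainly meant. Section 6.3 sets the INS-212 EOT visit apart from a visit in INS-312, and INS-312 has its own Visit 1, called Baseline. Protocol 6.1 makes that the catch-up visit. Final SAP 3.1.3 equates Baseline with Day 1, and the Table 4 window ends on Day 1. The Month 1 reading conflicts with that window and with the pre-dose rule in 6.1, and it yields no Baseline at all for 6MWT, audiology, SGRQ, EQ-5D-3L or the biomarkers. For vital signs, the split by timepoint in 9.6 makes averaging an unlikely choice, and the table mock-ups, which are separate documents, may settle it.

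Most of this stands. Visit 1 is the more natural reading, and completing the INS-212 EOT visit is an entry criterion (Protocol 4.1), so few values should be missing. It does not close the gap. Section 6.3 does not refer to Table 4, and that window includes Day 1 with no pre-dose limit. The pre-dose rule in 6.1 covers unscheduled visits only. Section 9.6 does not say whether a post-dose change is taken from a pre-dose or a post-dose Baseline.

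The first-analysis SAP (10.2, 13.3, 13.4 and 13.6) limits Baseline to values up to first dose. It governs a different analysis, so it shows only that the condition is absent from the final text, not that the final text is contradicted.

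**Conclusion.** The fallback sentence is wrong as written, and the point is minor. It can turn an on-treatment value into a Baseline, and even on the likelier reading it does not identify the Day 1 vital-sign and oximetry Baseline. Over the assumed range the expected misplacement is at most 1 subject in about 200, and the oximetry mean moves by at most 0.15 points. These sizes rest on assumed missingness, shift rates and dose effects. Probably only a very few subjects are involved: those without an INS-212 EOT value and, for the Month 1 problem, in the main those with none at Visit 1 either.

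Three stronger conclusions might be inferred, and the documents do not support them:

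- *The primary safety endpoint is compromised.* Observed values by visit, the number of high results at each visit and the adverse event tables do not use Baseline. In a shift table only the Baseline row changes. No hypothesis is tested (final SAP 8.2).
- *6MWT, audiology or questionnaires would take a Month 6 Baseline.* That needs a rule of using the next visit that has a value, which 6.3 does not state.
- *Hearing loss is materially under-reported through the Grade 0 default in final SAP 6.4.8.* A pre-dose Day 1 audiogram is required, and final SAP 9.7 tabulates only subjects with data at the visit. What remains is an edge case: a post-baseline audiogram with no baseline one.

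**What to change.** Keep the first sentence of 6.3 and replace the second with:

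> If that value is missing, Baseline is the last non-missing value (scheduled or unscheduled) obtained before the first INS-312 dose; for vital signs and oximetry, the pre-dose value. If there is none, Baseline and change from Baseline are missing (6.4.6). CT sub-study scans keep their protocol Baseline window.

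The CT exception is needed because Protocol Appendices 3 and 4 allow a Baseline scan up to 14 days after Day 1. Do not add the Day -2 to 1 limit from Table 4: section 6.1 accepts any last pre-dose unscheduled value, and a window here would conflict with it.

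An optional companion change to 6.4.8: show a subject with a post-baseline but no baseline audiogram as not gradable rather than Grade 0, unless the absolute Grade 4 criterion is met.

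The cost is one sentence and one derivation, plus one table row if 6.4.8 is clarified. The downside is that a few subjects may drop out of the change-from-baseline rows. No clinical procedure changes.
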